6.0 UNANTICIPATED PROBLEMS

6.1 Definition

As defined by UNC's IRB, unanticipated problems involving risks to study subjects or others (UPIRSO) refers to any incident, experience, or outcome that:

- Is unexpected (in terms of nature, severity, or frequency) given (a) the research procedures that are described in the protocol-related documents, such as the IRB-approved research protocol and informed consent document; and (b) the characteristics of the subject population being studied;
- Is related or possibly related to a subject's participation in the research; and
- Suggests that the research places subjects or others at a greater risk of harm (including physical, psychological, economic, or social harm) related to the research than was previously known or recognized.

6.2 Reporting

Any UPIRSO that occurs during the conduct of this study and that meets all three criteria listed in 6.1 must be reported to the UNC IRB using the IRB's web-based reporting system. The PI will also report any UPIRSO to the PCRC and the NINR. The PI will be responsible for assessing developments in the literature and results of related studies by conducting a literature review once during the grant period to identify relevant information that may impact the safety of participants or on the ethics for the research study.

7.0 STATISTICAL CONSIDERATIONS

7.1 Study Design

This is a mixed methods pilot study designed to evaluate the content validity of the BWS survey.

7.2 Sample Size and Accrual

Our primary objective is to establish content validity of the BWS survey. Based on established guidelines, 7-10 participants are needed to establish content validity of survey items in cognitive interviews.⁴¹⁻⁴³ As we will be stratifying patients for cognitive interviews into 2 groups, we will have 10 participants per stratification to ensure saturation in both.

Based on our prior data, we anticipate that we will have a 3:1 split between patients who value living longer most and those who value another attribute most. Therefore, we will need to recruit at least 40 patients to have 10 patients who value another attribute most to participate in cognitive interviews. Accounting for variability and drop out, we will plan to recruit 50 patients total to be able to recruit 10 patients in this group.

10 clinicians will provide for saturation for qualitative interviews.

This study was not designed to be powered to evaluate secondary endpoints or exploratory endpoints.

We expect to accrue up to 50 patients over the time of the study. We see over 500 new patients with hematologic malignancies per year within the division of hematology.

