1.0 BACKGROUND AND RATIONALE

1.1 Study Synopsis

This study will evaluate the content validity of using a survey to quantify patient preferences at the point-of-care for newly-diagnosed patients with hematologic malignancies. Our primary hypothesis is that by identifying the strength of patient preferences for outcomes with this survey, clinicians will be able to improve goal-concordant care by aligning clinical recommendations with patients' preferences. We will conduct cognitive interviews with 20 patients to establish the content validity of the survey. We will use purposive sampling based on the results of the survey to create two groups of patients (n=10 each) for the cognitive interviews. We plan to recruit 50 total patients to complete the survey to ensure adequate recruitment in each group. Secondary outcomes will evaluate acceptability and feasibility of administering the survey. The information we obtain from these participants will be used to refine the survey. Interviews with oncologists and palliative care specialists (up to 10) will inform implementation.

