4.2 Duration of Study

The recruitment is planned to last for up to 24 months. Patients will complete the survey instruments up to 6 times over 3 months (Longitudinal Assessments) and then every 3 months for up to 2 years (7 times) (Extended Assessments). Patients will complete qualitative interviews within 3 months of treatment decision. Clinicians will be interviewed once over the course of the study.

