4.3 Study Details

4.3.1 The study will recruit 50 total participants and conduct qualitative interviews on a subset of 20 participants.

4.3.2 **Pilot testing:** The study team will review the inpatient census and clinic schedule to evaluate for potentially eligible patients. The study team will confirm patient eligibility with the primary oncologist or principal investigator. Eligible patients will be sequentially approached to be recruited to this study until 50 patients are recruited who complete BWS survey.

Upon enrollment, the study team will record information about patients obtained from the patient or the medical record including gender, age, lab values including complete metabolic profile, complete and differentiated blood counts, albumin, LDH, a1c, cholesterol levels, hematopathology reports, clinician-determined performance status (Karnofsky and ECOG), and comorbidities present.

Demographic information such as age, sex, and zip code will be obtained.

Once consented, patients will complete initial study questionnaires within PRO Core either remotely if able or in-person with the assistance of study staff prior to a clinic visit. For patients who decline to participate in the study, reasons for refusal will be anonymously collected to examine the issue of selection bias as well as to assist with determination of feasibility.

After the clinic visit, patients will be prompted to complete the first longitudinal assessment via PRO Core. This will be available for 7 days. The treating oncologist who saw the patient will be prompted to fill out an assessment via email. Clinicians may receive multiple reminder emails to complete the survey to improve completion rates. We will collect provider responses within 2 weeks of initial patient survey.

Following, every 2 weeks (up to 5 times) participants will be prompted in PRO Core to complete the longitudinal assessment survey. Then, the extended assessment survey will be delivered by PRO Core every 3 months for up to 2 years (7 times).

Retention:

Multiple strategies will be utilized to retain patients on study.

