Staff will setup a time to interview eligible participants. Interviews will be scheduled within 14 days of the treatment decision (+ 14 days). A reminder email and/or phone call will be sent to participants the day before and the day of the interview. If participants do not respond during the pre-scheduled time, staff will reschedule the interview/reminders. Participants will be provided with a \$25 gift card following completion of the interview.

Follow-up interviews will be around 3 months after the initial interview (+ 30 days). Interviews will follow the same format as the initial interview. Participants will be provided with a \$25 gift card following completion of the interview.

Interviews will also be completed with up to 5 oncology clinicians and up to 5 palliative care clinicians. Clinicians will be referred to the study staff by the principal investigator. Interviews will take place over the course of 1 year and will not be time dependent upon patient enrollment. Participants will be provided with a \$25 gift card following completion of the interview.

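### Do 50 survey completers leave room for both chance variation and drop-out when 10 interviews are wanted in the smaller preference group?

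*Combined protocol and SAP*

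**What the plan says.** The primary aim is content validity, studied in 20 cognitive interviews, 10 in each of two groups: patients whose most important attribute is living longer, and patients who put some other attribute first (sections 4.3.3 and 4.3.4). Section 7.2 says that published guidance calls for 7 to 10 interviews and that "we will have 10 participants per stratification to ensure saturation in both".

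Section 7.2 then takes a 3:1 split from prior data, derives a minimum of 40 patients, and adds an allowance: "Accounting for variability and drop out, we will plan to recruit 50 patients total to be able to recruit 10 patients in this group". The synopsis (1.1) puts the purpose more firmly: "We plan to recruit 50 total patients to complete the survey to ensure adequate recruitment in each group".

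On who counts towards the 50, section 4.3.2 says: "Eligible patients will be sequentially approached to be recruited to this study until 50 patients are recruited who complete BWS survey". Section 7.2 adds "We expect to accrue up to 50 patients over the time of the study". Section 4.3.3 has staff phone eligible consented patients until the 20 interview places are filled, with the first interview within 14 days (plus a further 14) of the treatment decision. No section says what happens if the smaller group runs out.

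**The concern.** The smaller group sets the sample size, and the step from 40 to 50 is said to cover two things without a figure for either. Forty is only the number whose average yield is 10; the chance of actually reaching 10 with 40 patients is 56%. The step to 50 is exactly what a 20% drop-out allowance alone would give (40/0.80 = 50), leaving nothing for chance. Conversely, if 80% assurance is wanted against chance alone, 49 patients are needed and one is left for drop-out.

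Since the 50 are survey completers, loss before the survey is replaced. The exposed loss falls between the survey and the interview, and accrual has stopped by the time the last of it is known. If the smaller group ended below 10, the plan's own number for saturation in that group would be missed with no stated way to respond, although "We see over 500 new patients with hematologic malignancies per year within the division of hematology" and the recruitment period is up to 24 months. That would bear on the primary objective.

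**Working it through.** **Inputs.** From section 7.2: share of the smaller group p = 0.25 (3:1 split), target 10, guidance range 7 to 10, accrual 50. From section 4.3.2: the 50 are survey completers. Assumed: loss d between survey and interview. The documents give no interview loss rate. The only attrition figure is the 5-7% missing data in section 7.3.2, stated for the first longitudinal questionnaire; it is borrowed here as one assumption, with 10% and 20% as wider ones.

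**The plan's own figure.** 10/0.25 = 40, which reproduces. At 50 the expected number is 50 × 0.25 = 12.5, so there are 2.5 spare patients on average for 10 places.

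**Chance of reaching 10.** Let X be the number in the smaller group who are interviewed, X ~ Binomial(n, q), with q = 0.25 × (1 − d).

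With no loss, P(X ≥ 10) is 56.1% at n = 40, 79.5% at 48, 81.7% at 49 and 83.6% at 50. The smallest n for a given assurance is 45 for 70%, 47 for 75%, 49 for 80%, 55 for 90% and 60 for 95%. How much of the margin remains for drop-out therefore depends wholly on the assurance level chosen, and the plan chooses none.

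**Adding loss, n = 50.**

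| Loss before interview | q | P(at least 10) | P(at least 7) |
|---|---|---|---|
| 0% | 0.2500 | 83.6% | 98.1% |
| 5% | 0.2375 | 78.2% | between 95.3% and 98.1% |
| 7% | 0.2325 | 75.7% | between 95.3% and 98.1% |
| 10% | 0.2250 | 71.6% | 95.3% |
| 20% | 0.2000 | 55.6% | 89.7% |

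**Size of a shortfall.** With no loss, P(X < 10) = 1 − 0.836 = 16.4%. Of this, P(7 ≤ X ≤ 9) = 0.981 − 0.836 = 14.4 percentage points, so about 88% of shortfalls (14.4/16.4) stay inside the 7-10 range. At 10% loss the figures are 28.4% and 0.953 − 0.716 = 23.7 points, or about 83%. At 20% loss they are 44.4% and 0.897 − 0.556 = 34.0 points (from unrounded values), or about 77%.

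**What more accrual would buy.** Continuing to at most 60 completers only when short raises 83.6%, 71.6% and 55.6% to 95.5%, 89.5% and 78.7%, at an average over all cases of 1.0, 1.9 and 3.3 extra patients. When the extension is actually used (no loss), the average is 1.00/0.164 = 6.1 extra patients, of whom 6.1 × 0.25 = 1.5 belong to the group that is short.

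**The case for a change.** The strongest case for a change is this. Ten, not seven, is the number the plan chose, and the synopsis speaks of ensuring it. Even the mild 5-7% loss takes the chance of reaching 10 below 80%, and stricter readings of ensuring need 55 or 60 patients before any loss. The 25% share is itself uncertain: the one earlier survey of this type that the plan describes was in AML (4.3.5), while 30 of the 50 planned patients are outside the acute leukemia stratum (4.3.4). At an illustrative 20% share the chance of reaching 10 is 55.6% with no loss. A contingent extension would be feasible, and a reporting sentence costs almost nothing.

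Part of this stands. The probabilities are correct, the margin is not generous, and no rule covers exhaustion of the smaller group. Three things limit it. First, the 80% benchmark is the reader's; 50 completers give 72% at 10% loss, so the margin does absorb some of both. Second, individual refusals are replaced, because staff keep calling eligible patients, so only an exhausted pool is uncovered. Third, uncertainty in the share runs both ways: at 30% the chance is 96.0% with no loss. Section 7.2 does not say which prior data gave 3:1, so a transfer from AML cannot be established. Even at a 20% share with no loss, at least 7 interviews are reached with probability 89.7%.

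**Conclusion.** No change is called for. The arithmetic in section 7.2 is right, the wording about variability and drop-out is loose rather than false, and no stated assurance is missed. At the plan's 3:1 split, 50 completers give at least 10 interviews in the smaller group with probability 84% with no loss, 78-76% at a borrowed 5-7% loss and 72% at an assumed 10%. They give at least 7, the lower end of the range the plan cites as enough, with probability 98% with no loss and 95% at 10%.

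This is a pilot, and the content-validity analysis in section 7.3.1 is a narrative synthesis with no threshold at 10. With 8 or 9 interviews in one group, analysts would report the count and say whether new comprehension problems were still emerging; writing that down beforehand would alter no result. Raising the ceiling would mean approval of a higher accrual limit and keeping later patients out of the denominators of 50 in section 7.3.2, mostly by enrolling patients outside the group that is short. Stopping at 50 is a fair trade-off.

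The conclusion rests on the 25% share and on the assumed loss rates. At 20% loss the chance of 10 falls to 56%, but the chance of at least 7 is still 90%.

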7.3 Data Analysis Plans

7.3.1 Primary Aim: Content Validity

The primary aim of this study is to evaluate the content validity of the BWS survey. This will be established by mixed methods. We will conduct cognitive interviews with patients in accordance with FDA guidance on patient-reported outcomes measurement development to evaluate patient understanding of each concept within the BWS and explore other areas that were important but were not included in the survey.⁴¹ We will produce a cognitive interview summary based on published guidance to determine content validity from the interviews.⁴¹ Additional interview questions from the qualitative interview will be used to establish the importance of individual attributes to patients using interpretive phenomenological analysis (IPA)⁴⁴ and provide additional support to BWS content validity. Results from the ranking exercise (embedded within the BWS survey) will also be reported. To integrate data from each source, we will follow a sequential explanatory approach: we will produce narrative summaries of each aspect of the critical determinants identified in interviews followed by a summary of both quantitative and qualitative data. Together, these data will provide convergent support of the content validity of the BWS survey.

7.3.2 Secondary Aims

Patient acceptability:

We will conclude the BWS is acceptable if $\geq 70\%$ of patients (35/50) report that it is acceptable. Hypothesizing 80%, the exact binomial 95% CI will be 66.3-90.0%.

Preliminary efficacy:

We will conclude the tool is potentially efficacious if efficacy (defined as participants answering “moderately effective/very effective” to the question: “How effective was the survey to help you and your doctor choose a treatment that was consistent with your goals?”) is reached in $>50\%$ of patients. Estimating 5-7% missing data from enrollment to initial longitudinal questionnaire (from other PRO assessments in advanced cancer patients^{45,46}) and hypothesizing a rate of 75%, the exact binomial 95% CI will be 60.0-86.6%.

Preliminary completion rates:

Frequencies will be reported at each time point. Completion rate out of the original 50 participants will be reported at each month with exact binomial 95% CIs with reasonable precision, no wider than $\pm 14.5\%$. Reasons for dropout will be summarized as available. Associations of baseline patient characteristics with completion rates will be explored using Wilcoxon Rank sum and Kruskal-Wallis tests.

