3.0 PARTICIPANT ELIGIBILITY

3.1 Inclusion Criteria

Patients must meet all of the inclusion criteria listed below to participate in the study.

- have a confirmed new diagnosis of the following hematologic malignancies:
 - Aggressive lymphoma (including, but not exclusive of, diffuse large B-cell lymphoma, advanced stage Hodgkin’s lymphoma, Burkitt lymphoma, double hit lymphoma, mantle cell lymphoma)
 - multiple myeloma
 - chronic lymphocytic leukemia
 - chronic myeloid leukemia
 - acute myeloid leukemia
 - acute lymphoblastic leukemia
 - myelodysplastic syndrome with excess blasts (MDS EB1 or MDS EB2)
- Age ≥ 60
- Ability to read, understand, and communicate fluently in English
- Ability to understand and comply with study procedures

- Willingness and ability to provide written informed consent

Patients will become eligible for enrollment upon pathologic confirmation.

Patients will be eligible for enrollment for 28 days after confirmatory diagnosis or until the start of chemotherapy.

Chemotherapy will not include hydroxyurea, cyclophosphamide, or cytarabine if used only for emergent cytoreduction.

Health care clinicians must be employed in hematology/oncology or palliative care as a nurse navigator, advanced practitioner, and/or physician. Together, these participants will be referred to as healthcare clinicians.

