4.0 STUDY PLAN

4.1 Schema

- 4.1.1 This study will evaluate the validity of using this out(BWS) survey to quantify patient preferences at the point-of-care and the potential effectiveness of the survey to improve goal-concordant care. Our primary hypothesis is that by identifying the strength of patient preferences for outcomes with this survey, clinicians will be able to improve goal-concordant care by aligning clinical recommendations with patients' preferences.

Within this study we aim to evaluate the content validity, acceptability, and potential effectiveness of the BWS survey to improve goal-concordant care. Using the BWS survey, we will collect the preferences of 50 older (>60 years) newly-diagnosed hematologic cancer patients facing treatment decisions and evaluate content and construct validity of the survey, patient acceptability, and

effect of preference elicitation on patient-reported quality of treatment decisions (effectiveness). Qualitative interviews involving cognitive interview questions (n=20) with patients will further explore the content validity of the survey and potential effect of the surveys on goal-concordant care. Interviews with palliative care clinicians, and oncologists will explore barriers and facilitators of implementation.

We also aim to describe how patients' preferences change over time and explore potential relationships between patients' preferences and clinical outcomes. We will collect the preferences of the patients with hematologic cancer every other week for 3 months (repeat sampling up 5 times) and then every 3 months thereafter for up to 2 years. We will describe changes in preferences at each timepoint. An exploratory, hypothesis-generating analysis will evaluate correlations between preferences and standard clinical outcomes (e.g. treatment intensity and response), symptoms (collected with the PRO-CTCAE), health-related quality of life (EQ-5D), and decisional satisfaction to provide direction for future studies.

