4.1.2 Trial Schema outline (patients)

Clinical Timeline:	New Diagnosis	Clinic Visit: Treatment Decision	Within 14 days of treatment decision	3 months after treatment decision	Every 2 weeks after LA 1	Every 3 months after LA 1
Study Activity:	Enrollment, Complete BWS, Baseline Questionnaire	Longitudinal Assessment (LA) 1: BWS, Follow-up Questionnaire	Cognitive and Qualitative Interview	Cognitive and Qualitative Interview	Longitudinal Assessments 2 - 6	Extended Assessments 1 - 7
Domains assessed:	Baseline Preferences, HRQoL, Symptoms, Decisional Conflict	Acceptability, Prelim efficacy, Preferences, Communication, Decision Regret, Follow-up domains	Content validity	Content validity	Preferences, Communication, Decision Regret, Follow-up domains	Preferences, Communication, Decision Regret, Follow-up domains

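### Should the >50% preliminary-efficacy rule be limited to patients whose first BWS preceded the treatment decision?

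*Combined protocol and SAP*

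**What the plan says.** Section 7.3.2 opens the rule with "We will conclude the tool is potentially efficacious if efficacy" and sets the bar at more than 50% of patients giving one of the two favourable answers to "How effective was the survey to help you and your doctor choose a treatment that was consistent with your goals". The only loss it plans for is given as "Estimating 5-7% missing data from enrollment to initial longitudinal questionnaire". At a hypothesised 75% it quotes an exact 95% interval of 60.0-86.6%. It names no analysis set and no order condition.

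Four places govern timing:

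- Section 4.1.1 describes the population as "newly-diagnosed hematologic cancer patients facing treatment decisions".
- The schema in 4.1.2 puts enrolment and the first BWS at new diagnosis, then the column "Clinic Visit: Treatment Decision", where Longitudinal Assessment 1 (LA 1) and the efficacy item sit.
- Section 4.3.2 has the initial questionnaires done "either remotely if able or in-person with the assistance of study staff prior to a clinic visit", and continues: "After the clinic visit, patients will be prompted to complete the first longitudinal assessment via PRO Core".
- Section 4.3.6 starts the longitudinal assessments once treatment has been discussed with the oncology clinician.

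Two places are looser. Section 3.1 states "Patients will be eligible for enrollment for 28 days after confirmatory diagnosis or until the start of chemotherapy". Table 5.1 has an Interim column for a BWS missed at enrolment and does not define Interim.

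**The concern.** The efficacy item presupposes that the survey came before the treatment choice. Section 3.1 closes enrolment at the start of chemotherapy, not at the decision, so a patient with a treatment chosen but not begun could enrol. Section 4.3.2 also screens the inpatient census, where the phrase about a clinic visit fits less well. Interim completion is not tied to the decision. LA 1 itself contains a BWS, so a patient who missed the earlier one could meet the survey for the first time after the decision and rate its effect on that decision in the same sitting.

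Such answers would be pooled with those of patients the survey could have helped, and the pooled rate carries a pass/fail conclusion. The bias could run either way.

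**Working it through.** **Inputs.** From 7.3.2: 50 patients, 5-7% missing, hypothesised rate 75%, threshold above 50%. From 7.2: secondary endpoints are not powered. Assumed, because the documents do not give it: m, the number of responders first surveyed after the decision.

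**The plan's own figure.** Responders expected: 50 × 0.93 = 46.5 to 50 × 0.95 = 47.5. The Clopper-Pearson interval at 75% with n = 46 (34.5 events) is 60.0-86.6%, as stated; n = 47 (35.25 events) gives 60.2-86.5%. The interval therefore implies about 46 responders, although 7.3.2 does not state the denominator. With 46 the rule needs 24 favourable answers.

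**When could restricting the set alter the conclusion?** Let X of 46 answer favourably, k of them among the m late patients. The all-responder rule passes if X/46 > 0.5; the restricted rule passes if (X − k)/(46 − m) > 0.5. Trying every possible k gives the values of X at which the two can disagree:

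| m (assumed) | X where they can disagree | X/46 |
|---|---|---|
| 3 | 22-24 | 48-52% |
| 5 | 21-25 | 46-54% |
| 9 | 19-27 | 41-59% |
| 14 | 17-30 | 37-65% |

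For m = 5, the upper end is X = 25, k = 5: 25/46 = 54.3% passes and 20/41 = 48.8% fails. The lower end is X = 21, k = 0: 21/46 = 45.7% fails and 21/41 = 51.2% passes. These are extreme cases over all possible answers.

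**Near the hypothesised 75%.** At X = 34 with every late patient favourable, m = 21 leaves 13/25 = 52.0% (passes) and m = 22 leaves 12/24 = 50.0% (fails). At X = 35, m = 23 leaves 12/23 = 52.2% (passes) and m = 24 leaves 11/22 = 50.0% (fails).

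**If the denominator were 50,** as in the acceptability rule (35/50), the threshold would be 26. The range for m = 3 becomes 24-26 and for m = 5 becomes 23-27. The picture is the same.

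**Direction.** Take 47 responders, 10 of them late, with a true favourable rate of 45% in the other 37 (assumed). The restricted rule (19 of 37) passes with probability 0.27. The all-responder rule (24 of 47) passes with probability 0.58 if late patients are favourable at 75%, and 0.10 if at 25%. With a true 75% in the 37, the restricted rule passes with probability 0.999, and the all-responder rule still with 0.987 when late patients are favourable at only 25%.

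**The case for a change.** The strongest case for a change is that enrolling after the decision but before chemotherapy is not even a deviation: it meets 3.1 as written. Section 7.3.2 attaches a formal conclusion to the item, so its denominator ought to match the question. A set chosen after the answers are seen would be open to challenge. The remedy looks cheap: two dates, one footnote and one sentence, with little loss of precision (30/40 gives 58.8-87.3%).

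Part of this stands. The text has no order condition, Interim is undefined, the denominator must be inferred, and close to 50% a handful of late patients could tip the result.

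The rest is weaker. The eligibility window is an outer limit; it does not replace the schedule. The visit in 4.3.2 is the one followed by LA 1, which the schema labels as the decision visit and the retention list treats as the treatment encounter. A late first survey is also not necessarily useless, since a decision can take several visits and stay open until treatment starts. Finally, failing to reach a patient in time is part of how a point-of-care tool performs. Dropping such patients selects on successful delivery. If they rate the survey low, restriction raises the chance of passing, from 0.10 to 0.27 in the example above. Keeping all responders and showing the on-time patients alongside is at least as defensible.

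**Conclusion.** No change is needed. The omission is real on paper, but the plan already intends the right order, and writing down a definition of Interim would only record it. Limiting the rule to on-time patients is a trade-off, not a correction: it sharpens the match with the question and gives up the view of performance as delivered.

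The likely effect is small. At the hypothesised 75% the conclusion holds unless at least 22 of 46 responders were late and all favourable. With 5 late it is in doubt only between 21 and 25 favourable answers. This rests on an assumed m and on about 46 responders. The response options in Appendix 9 are not shown, so a not-applicable answer cannot be ruled out.

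Analysts can fill the gap sensibly. The LA 1 prompt, the next-day reminder and the interview window all depend on the date of the visit or decision, so counting late patients and giving the on-time rate beside the main one should need little new data. The primary content-validity aim, acceptability, completion rates and the stated interval are unaffected.
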